12.3	SUBJECT STIPENDS OR PAYMENTS.....	17
13	PUBLICATION PLAN	17
14	REFERENCES.....	17
15	ATTACHMENTS	18

CONFIDENTIAL

List of Abbreviations

actinic keratosis (AK)
human papilloma virus (HPV)
Toll-like-receptor-7 (TLR7)

CONFIDENTIAL

Study Summary

Title	Open-label, single-arm pilot study of the effects of topical 5% Imiquimod cream on preventing keloid recurrence after surgical keloidectomy
Short Title	Imiquimod for preventing keloid recurrence
IRB Protocol Number	
Phase	Pilot study
Methodology	Open-label, single-arm
Study Duration	Enrollment of patient will take place over the next year. The project will begin as soon as the IRB is approved.
Study Center(s)	Single-center
Objectives	
Primary objective:
 
 - To assess the efficacy of topical 5% Imiquimod cream on decreasing keloid recurrence after excision. 
Secondary objectives:
 
 - To assess the tolerability of topical 5% Imiquimod cream
Number of Subjects	10
Diagnosis and Main Inclusion Criteria	
Key inclusion criteria Patients age ≥ 18 with keloids $< 5\text{cm}$ on trunk (below neck and excluding groin) and extremities (excluding hands and feet) requesting excision Able and willing to provide informed consent
 
Key exclusion criteria Pregnant or breastfeeding Taking systemic immunosuppressive medication, life threatening disease, or inherent sun-sensitivity Hypersensitivity to study drug Age < 18 Keloids located in sections as noted above Unable to follow-up for 10 weeks Involvement in a trial of another experimental intervention within 30 days Unable or unwilling to provide informed consent

Study Product, Dose, Route, Regimen	5% Imiquimod cream, topical application to cover skin lesion once daily x 5 days per week for 6 weeks
Duration of administration	6 weeks
Reference therapy	None
Statistical Methodology	Response rate will be presented as a percentage, with 95% confidence intervals. Other endpoints will be presented descriptively, with an appropriate measure of variation (e.g. standard deviation) if necessary.

CONFIDENTIAL

1 Introduction

This document is a protocol for a human research study. This study is to be conducted according to US and international standards of Good Clinical Practice (FDA Title 21 part 312 and International Conference on Harmonization guidelines), applicable government regulations and Institutional research policies and procedures.

This is an open-label, single-arm, pilot study on the effects of topical imiquimod treatment in preventing keloid recurrence after surgical excision. Keloids are abnormal scars that form in certain genetically predisposed individuals following trauma to the skin. They can be physically disabling and cause social impairment. Many therapies have been proposed and trialed for the permanent removal of keloids, but they all have limited efficacy. (1)

Topical imiquimod therapy has been reported to decrease keloid recurrence following keloidectomy in human patients (8-13). In our lab, we observed that topical imiquimod pre-treatment (imiquimod initiated prior to onset of trauma) improves wound closure and decreases scar formation in mouse ear-punch models of wound healing. Given all previous reports of adjuvant imiquimod therapy to keloidectomy initiated imiquimod therapy after keloidectomy, we would like to test the efficacy of topical imiquimod pre-treatment in preventing keloid recurrence after surgical excision.

1.1 Background

Keloids are benign dermal fibroproliferative tumors that represent a form of abnormal wound healing following any insult to the deep dermis, including lacerations, abrasions, surgery, piercings, vaccinations, and burns in predisposed individuals (1). They are distinguished from hypertrophic scars, another type of abnormal scar formation, by their extension beyond the borders of the original wound, failure to regress spontaneously, and tendency to recur following excision (1).

Keloids tend to occur more frequently in dark-skinned individuals, with an incidence of up to 16% in those of black and Hispanic backgrounds (2). These lesions appear to affect male and female subjects equally and most commonly occur in persons aged 10-30 years (2). They typically form on the ears, face, chest, and shoulders and can cause pain, burning, itching, and restriction of motion. Furthermore, the scars can be extremely disfiguring and potentially cause significant social and psychological distress in affected individuals.

The process by which keloids develop is poorly understood, though most theories of keloid etiology relate to fibroblast dysfunction (2). These lesions are difficult to treat, as they frequently recur following excisional removal. Current treatment options include surgical excision, laser, intralesional injections, pressure and silicone dressings, topical preparations, oral agents, radiation, and cryotherapy (1). Oftentimes, surgical excision is combined with adjuvant therapies such as corticosteroids and immunomodulators at the time of skin closure because surgical excision alone has recurrence rates ranging between 45% and 100% (3). Additionally, because surgical excision requires complete removal of all abnormal tissue, post-excision keloid recurrence may lead to a larger keloid than prior to excision. Although many adjuvant therapies to surgical excision and modalities for keloid removal have been proposed, there has been no consensus regarding how to best treat these lesions, and there is currently no medication approved for the indication of reducing keloid recurrence after excision.

Imiquimod is an immunomodulating agent that binds to Toll-like-receptor-7 (TLR7) and acts as a potent inducer of interferon and cytokine release at the site of skin application. It has been shown to decrease excessive collagen production and upregulate certain apoptosis-related genes in keloid fibroblasts (4). When formulated as a 5% cream, Imiquimod is a safe and well-tolerated drug. Side effects include skin erosion, excoriation, flaking, and edema at site of application (5).

CONFIDENTIAL

1.2 Investigational Agent

Imiquimod is an immune response modifier that binds to TLR7 and, when applied topically to the skin, induces the production of a variety of cytokines (6). It is manufactured as a cream at concentrations of 2.5%, 3.75%, and 5%. 5% Imiquimod is currently approved for the treatment of actinic keratosis (AK), superficial basal cell carcinoma, and external genital and perianal warts (condylomata acuminata) from human papilloma virus (HPV) infection (7).

Imiquimod is applied topically, and percutaneous absorption of Imiquimod is minimal. 5% Imiquimod cream will be used in this study. Each gram of 5% Imiquimod cream contains 50 mg of Imiquimod in an off-white oil-in-water vanishing cream base consisting of isostearic acid, cetyl alcohol, stearyl alcohol, white petrolatum, polysorbate 60, sorbitan monostearate, glycerin, xanthan gum, purified water, benzyl alcohol, methylparaben, and propylparaben (7).

A mean peak serum drug concentration of 0.4 ng/ml was observed in a small study of 12 patients with genital/perianal warts following an average applied dose of 4.6 mg. In patients with actinic keratosis who applied 5% Imiquimod cream topically 3-times weekly for 16 weeks, the mean peak drug concentrations at the end of week 16 were approximately 0.1, 0.2, and 3.5 ng/mL for applications to face (12.5 mg Imiquimod), scalp (25 mg Imiquimod), and hands/arms (75 mg Imiquimod), respectively. After up to 3 weeks of dosing with the 3.75% cream (18.75 mg/day applied to the face and scalp) in 17 patients with actinic keratosis, the mean peak serum Imiquimod concentration was 0.323 ng/mL with a median t_{max} of 9 hours after dosing. It appears that systemic exposure may be more dependent upon surface area of application than amount of applied dose. The half-life of the 3.75% cream was 29.3 +/- 17 hours at the end of the study; therefore, steady-state concentrations are anticipated to occur by day 7 with once daily dosing. The apparent half-life of the 5% cream was about 10-times greater with topical dosing than the 2-hour apparent half-life seen following subcutaneous dosing, suggesting prolonged retention in the skin. (7) (16)

1.3 Preclinical Data

Multiple case reports have suggested that Imiquimod application to the sites of surgical wounds and to hypertrophic scars may reduce scar occurrence/recurrence. In our lab, we have shown that topical application of 5% Imiquimod increases the rate of wound closure and leads to increased tissue regeneration with decreases in scarring in mouse ear hole punch models of tissue regeneration. In our preclinical study, we applied 5% Imiquimod cream for 5 days one week prior to ear hole punch (**Figure 1A**). In the presence of Imiquimod, there is a marked increase in the rate of closure when compared to control (**Figure 1C**) often leading to complete closure of the wound (**Figure 1B, D**). The drug treated group also demonstrates more complete regeneration of skin appendages such as sebaceous glands (arrowhead) and ear cartilage (arrow) in the new tissue (**Figure 1D**), a feature consistent with tissue regeneration and not scar formation.

To eliminate the possibility that this Imiquimod phenotype is simply due to nonspecific skin irritation, other skin irritants such as calcipotriol and 12-O-tetradecanoylphorbol-13-acetate (TPA) were also tested. Wound closure rates were not significantly reduced compared to vehicle control in each case (data not shown).

These preliminary results suggest that Imiquimod application enhances wound closure and biases the healing process towards tissue regeneration and away from scarring.

[figure not shown]

Figure 1 Topical Imiquimod treatment improves mouse ear wound healing

CONFIDENTIAL

1.4 Clinical Data to Date

Case series and prospective trials of 5% Imiquimod after surgical keloidectomy have been reported. However, the results have been variable. As summarized in **Table 1**, post-excision treatment with Imiquimod appears to be most effective in preventing recurrence of keloids on the ears but has limited efficacy in other locations. Additionally, some studies were limited by poor patient follow-up compliance.

All of the reported studies were designed such that Imiquimod was started after surgical excision of keloids. There are no reports of initiating Imiquimod prior to surgical excision, and our preclinical data suggests that there may be a benefit to pre-excision Imiquimod therapy.

Table 1 Summary of published clinical data for Imiquimod therapy post-keloidectomy

Reference study	Number of keloids	Sites treated	Recurrence (%)	Follow-up duration
Berman (2002) (8)	11 (10 patients)	Earlobe (10) and back (1)	0 (0%)	24 weeks
Martin-Garcia (2005) (9)	8 (6 patients)	Earlobe	2 (25%)	24 weeks
Stashower (2006) (10)	8 (4 patients)	Earlobe	0 (0%)	12 months
Maholtra (2007) (11)	3 (2 patients)	Presternal	3 (100%)	12 weeks
Cacao (2009) (12)	9 (9 patients)	Trunk	8 (89%)	12 weeks
Frias (2018) (13)	41 (25 patients)	Trunk (9), suprapubic (2), extremity (4), auricular (20)	9 trunk (100%), 0 suprapubic (0%), 4 extremity (100%), 3 auricular (15%)	6 months

1.5 Dose Rationale and Risk/Benefits

Once daily application of 5% Imiquimod cream is currently approved by the FDA for the treatment of many skin disorders. Although the exact mechanism of action has not been elucidated, when used to treat pre-cancerous lesions and skin cancers, Imiquimod results in inflammation, which destroys the lesion and can result in complete regression. Additionally, as mentioned above, Imiquimod has been shown to be effective in preventing recurrence after surgical keloidectomy, though to a varying degree depending on the site of the lesion.

The proposed dosage regimen for this study is in accordance with the current recommended dosing for superficial basal cell carcinoma – apply once daily before bedtime 5-times per week for a total of 6 weeks. This regimen has been shown to be safe, tolerable as well as effective in inducing molecular and clinical responses in patients.

Areas treated with imiquimod may become inflamed. The symptoms may include itching, burning, redness, ulceration (sores), scabbing, flaking, and pain. There could be increased sensitivity to the sun in areas of drug application. This could be avoided by proper sun protection such as wearing protective clothing and/or applying sunscreen of SPF 30 or greater 15 minutes prior to sun exposure with reapplication every 2 hours. Systemic side effects may include “flu-like” symptoms such as fever, fatigue, headache, nausea, diarrhea, and muscle pain. These symptoms are less common and are generally mild.

Unlike previously reported studies, this study aims to initiate treatment with Imiquimod one week prior to keloidectomy. Our preclinical data suggests that pre-treatment with Imiquimod prior to injury increases wound healing and decreases scar formation. Additionally, it has been shown that when using

CONFIDENTIAL

corticosteroids as an adjunct to surgical excision, it is best to initiate treatment in the preoperative period and continue treatment for up to 3 months post-excision (14).

Because the effects of the drug are not well studied in pregnancy and during breastfeeding, it is possible that there are harmful side effects that are not yet known to both the mother and unborn or breast-feeding child. Therefore, pregnant and breastfeeding subjects are excluded from the study. Additionally, the risks of this study includes risks of breach of confidentiality. While every effort will be made to protect the confidentiality of study subjects, there is a potential risk of an inadvertent or unintended breach of confidentiality.

As demonstrated in patients who have used 5% Imiquimod for other FDA approved indications, risks of topical application of 5% imiquimod are minimal. Additionally, previous studies as well as our preclinical data indicates that 5% imiquimod could modulate wound healing and prevent keloid recurrence in patients when applied prior to keloid-excision and continued after the procedure. Therefore, we believe that the benefit of possible decrease in keloid recurrence outweighs the minimal risks posed by topical 5% imiquimod therapy.

2 Study Objectives

Primary Objective

To assess the efficacy of 5% Imiquimod cream on preventing keloid recurrence after excision. Subjects will be evaluated by a consultant dermatologist at 2, 4, and 8 weeks following excision and by phone 12 weeks after excision to assess for clinical evidence of lesion recurrence.

[figure not shown]
Secondary Objectives

To assess the safety and tolerability of 5% Imiquimod in subjects undergoing keloid excision. Subjects will be evaluated by a consultant dermatologist at 2, 4, and 8 weeks following excision to assess for local site reaction such as redness, discomfort, swelling, and ulceration.

3 Study Design

3.1 General Design

- Prospective, open-label, non-randomized, single-arm pilot study
- Subjects are expected to participate for a total of approximately 14 weeks from initial dermatology consultation visit

CONFIDENTIAL

3.2 Primary Study Endpoints

To assess the efficacy of 5% Imiquimod cream on decreasing keloid recurrence after excision when initiated prior to excision

3.3 Secondary Study Endpoints

To investigate the tolerability of 5% Imiquimod cream

3.4 Primary Safety Endpoints

To assess the safety and tolerability of 5% Imiquimod in subjects undergoing keloid excision.

At each clinic follow-up visit (2, 4, 8 weeks after excision), the investigator will rate the local site reaction on the following scale:

- None
- Mild reaction (slight redness, discomfort, no swelling, no ulceration)
- Moderate reaction (redness, pain and swelling, no ulceration)
- Severe reaction (redness, pain, swelling, and ulceration)

4 Subject Selection and Withdrawal

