5.2 Treatment Regimen

Topical dosage (5% cream)

Apply a thin coat of Imiquimod cream to cover the entire lesion once daily 5-times per week prior to normal sleeping hours, for 6 weeks, starting 1 week prior to keloid excision. Cream should be left in place for approximately 8 hours. The target keloid should have a maximum diameter of no more than 5cm and be located on the trunk (excluding anogenital skin), below the neck, or extremities (excluding hands or feet). The treatment area should include a 1 cm margin of skin around the tumor. The diameter of cream droplet applied should range from 5 mm to 10 mm for keloid areas of 0.5 cm to 5 cm, respectively. Subjects should wash hands thoroughly prior to and after application of medication. Maximum to be prescribed: 36 packets during the 6-week treatment period.

A rest period of several days during treatment may be required due to local skin reactions. Follow-up visits will be scheduled at 2, 4, and 8 weeks after excision and as needed for local skin reactions.

The following dosing algorithm will be used at the 2 and 4 visits and unscheduled visits due to local toxicity to adjust the frequency of application accordingly.

- If intolerable at 5 days per week; stop completely for 1 week then restart but at a reduced dose of 3 days per week. Increase to 5 days per week as soon as tolerable.
- If intolerable at 3 days per week, a further week off, start again at 3 days per week. Stop if intolerable.

Subjects will be requested to contact the local investigator for advice before stopping or changing treatment.

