5.9.4 Return or Destruction of Study Drug

At the completion of the study, subjects will be asked to return all unused medication at the final follow-up visit. There will be a final reconciliation of drug shipped, drug consumed, and drug remaining. This reconciliation will be logged on the drug reconciliation form, signed and dated. Any discrepancies noted will be investigated, resolved, and documented prior to return or destruction of unused study drug. Drug destroyed on site will be documented in the study files.

CONFIDENTIAL

6 Study Procedures

Patients will be recruited through the routine work of the Dermatology departments at the Hospital of the University of Pennsylvania. Recruitment and consent will be obtained by the principle investigator or another Dermatology physician as delegated by the investigator seeing the patient in the outpatient clinic. Patients seen in the outpatient clinic with clinical representation of keloids will be approached by the Dermatology attending as part of clinical evaluation, and written, informed consent will be obtained from the patient prior to any research related procedures are conducted.

It will be explained to the potential participant that entry into the trial is entirely voluntary and that their treatment and care will not be affected by their decision. It will also be explained that they can withdraw at any time. In the event of their withdrawal it will be explained that their data collected so far will be retained and used as part of the study analysis.

	Visit 1 (Week 1)	Visit 2 (Week 2)	Visit 3 (Week 4)	Visit 4 (Week 6)	Visit 5 (Week 10)	Phone encounter (Week 14)
Informed consent	X					
Urine pregnancy test	X					
Imiquimod application	X (start after visit)	X	X	X		
Keloid excision		X				
Excision specimen sent to pathology per SOC		X				
Photograph of lesion	X (optional)	X (optional)	X (optional)	X (optional)	X (optional)	
Evaluation of local site reaction		X	X	X	X	
Evaluation for recurrence			X	X	X	X

6.1 Visit 1

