6.2 Visit 2 – Procedure visit

Consent for and surgical removal of keloid will be performed in accordance with current standard of care. Keloid excision sample will be sent to pathology per standard of care.

6.3 Visits 3 and 4

Scheduled clinic visits will be at 2 and 4 weeks after the surgical excision (weeks 3 and 5 after initiation of Imiquimod). At these visits, the following will be recorded:

- Subject compliance with therapy – if doses were missed
- The investigator will evaluate for evidence of keloid recurrence
- The investigator will rate the local site reaction on the following scale:
 - None
 - Mild reaction (slight redness, discomfort, no swelling, no ulceration)
 - Moderate reaction (redness, pain and swelling, no ulceration)
 - Severe reaction (redness, pain, swelling, and ulceration)
- The dose of Imiquimod will be adjusted to according to the following algorithm:
 - If intolerable at 5 days per week; stop completely for 1 week then restart but at a reduced dose of 3 days per week. Increase to 5 days per week as soon as tolerable.
 - If intolerable at 3 days per week, a further week off, start again at 3 days per week. Stop if intolerable.
- Any new medication usage and health service usage data will be recorded.

6.4 Visit 5

Last scheduled clinic visit will be at 8 weeks after surgical excision (3 weeks after completing Imiquimod therapy). The investigator will evaluate for evidence of keloid recurrence at this visit and evaluate for any local site reactions per above.

If treatment of the lesion with Imiquimod is stopped because of local toxicity, this will prompt an unscheduled clinic visit so that the dose adjustment algorithm can be implemented.

If at any point during the treatment phase, the keloid is judged to have recurred, then the subject will progress immediately to intralesional injection or re-excision in accordance with current standard of care.

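### The four-level local reaction scale is not required at unscheduled toxicity visits or at the post-withdrawal visit, so the graded safety endpoint is likely to understate peak severity

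*Combined protocol and SAP*

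**What the plan says.** Section 3.4 holds the only named safety endpoint, a scale running from none through mild and moderate to severe. Ulceration appears only in the severe level. Its timing is: "At each clinic follow-up visit (2, 4, 8 weeks after excision), the investigator will rate the local site reaction on the following scale". The secondary objective in Section 2 names the same visits: "Subjects will be evaluated by a consultant dermatologist at 2, 4, and 8 weeks following excision to assess for local site reaction".

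The schedule table in Section 6 differs. Its row "Evaluation of local site reaction" is marked at Visit 2 (excision) as well as at Visits 3 to 5. The Visit 2 text in Section 6.2 covers surgery and pathology and mentions no rating. The table has no column for unscheduled visits.

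The plan expects visits outside this grid. Section 5.2 says: "Follow-up visits will be scheduled at 2, 4, and 8 weeks after excision and as needed for local skin reactions". Section 6.4 says that stopping for local toxicity leads to an extra visit, and gives its purpose: "this will prompt an unscheduled clinic visit so that the dose adjustment algorithm can be implemented". The first step of that algorithm (Sections 5.2 and 6.3) is: "If intolerable at 5 days per week; stop completely for 1 week then restart but at a reduced dose of 3 days per week". Section 4.4.2 adds one visit for withdrawn patients who have had at least one application, so that the site can be looked at. The scale is not named for either kind of visit.

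Section 7.2 reports endpoints other than response descriptively and defines no worst-grade summary. Section 7.3 limits the analysis to patients who completed the protocol.

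**The concern.** An unscheduled toxicity visit takes place because the patient could not tolerate the reaction. That is when a tolerability grade tells us most, and the plan does not ask for one. The next scheduled grade comes after drug has been stopped or only just restarted, when the site has had time to settle. Ratings missing for this reason are not missing at random; they are likeliest to be absent near the peak.

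At stake are the secondary objective and the safety endpoint. Rest periods, frequency reductions and permanent stops are direct evidence of poor tolerability, yet no stated endpoint counts them. The completers-only rule could push the same way if patients who stop for toxicity are treated as non-completers, which Section 7.3 does not settle.

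**Working it through.** **The plan's own figure.** The only computed figure is the sample size in Section 7.1. It supplies the denominators used below; the point does not otherwise depend on it. For a one-sample proportion with p0 = 0.70, p1 = 0.25, two-sided 5% (an assumption, as sidedness is not stated) and 80% power:

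n = [(1.960 × √(0.70 × 0.30) + 0.842 × √(0.25 × 0.75)) / (0.70 − 0.25)]² = 7.87, rounded up to 8.

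With 20% withdrawal, 8 / 0.80 = 10. Both stated figures reproduce.

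**Inputs for the timing check.**
- Scheduled ratings at 2, 4 and 8 weeks after excision: days 14, 28 and 56 (Sections 2 and 3.4).
- Post-excision treatment of 5 weeks (Section 6.1), so planned end at day 35.
- One week off after a stop (Sections 5.2 and 6.3).
- Possible stop days: days 1 to 34 without the rating days 14 and 28, which leaves 32.
- Assumption: rest weeks do not extend the treatment period. The plan does not say.

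**Gap = next rating day − stop day.**

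| Stop days | Next rating | Gap under 7 days | Exactly 7 days | 8 to 13 days | 22 to 27 days |
|---|---|---|---|---|---|
| 1–13 | day 14 | 6 | 1 | 6 | 0 |
| 15–27 | day 28 | 6 | 1 | 6 | 0 |
| 29–34 | day 56 | 0 | 0 | 0 | 6 |
| All 32 | | 12 | 2 | 12 | 6 |

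On 12 days the rating falls inside the week off. On 2 days it falls as that week ends. On 12 days it falls at most 13 − 7 = 6 days after the restart. On the last 6 days the week off runs past day 35, and the next rating is at week 8.

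**Week 8.** Week 8 − week 5 = 3 weeks after the planned end of treatment, for every patient. So 2 of the 3 ratings in Section 3.4 fall within post-excision treatment.

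**Pre-excision week.** For a stop 1 to 7 days before excision, the Visit 2 rating in the schedule comes 1 to 7 days later. If Visit 2 is not rated, the next rating is day 14, which is 15 to 21 days later.

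**Size.** The documents give no rate of unscheduled toxicity visits, so only the unit effect can be stated: 1/10 = 10 percentage points and 1/8 = 12.5 points per missed severe reaction. As an assumed range, with 0 to 3 of 10 patients having their only severe reaction between ratings, the true severe rate is 0% to 30%, while scheduled ratings could show 0/10 (exact 95% confidence interval 0% to 31%).

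**The case against.** The strongest case against is that little is lost, and some of it stands.

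- **A reader might infer that the reaction is rated only at weeks 2, 4 and 8.** The schedule also marks Visit 2, after the first treatment week. That conflicts with Sections 2, 3.4 and 6.2 and must be reconciled, but it does not reach the unscheduled visits.
- **A reader might infer that the next rating always follows a full week off drug.** On 12 of 32 stop days it falls inside that week, and a reaction may still be visible. The documents give no healing time.
- **A reader might infer that intolerable reactions go ungraded altogether.** Reactions present at the 2- and 4-week visits are graded there; Section 6.3 lists the rating ahead of the dose adjustment.
- **A reader might infer that the reactions are lost.** Section 8.2 requires adverse events to be sought at each contact, by examination where appropriate, and all to be recorded. Missed doses and compliance are also recorded (Sections 6.3 and 5.5). But Section 8 classifies events only as serious or non-serious, so a non-serious ulceration has no grade and no defined route into the endpoint.
- **Section 3.4 may already cover as-needed visits,** since Section 5.2 counts them as follow-up. Rating there is not forbidden. The list of weeks in Section 3.4 points the other way, however, and nothing requires it.
- **Intolerable is not defined as severe.** Moderate reactions could also trigger a visit, so not every missed rating is a missed severe grade.

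This is also a 10-patient pilot with descriptive reporting and no decision rule tied to the grade, which limits the consequences.

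**Conclusion.** The point holds as a gap in the graded endpoint, not in safety recording as a whole. Followed as written, the plan can leave the worst reactions between visits without a grade. The next scheduled grade is then made off drug or within 6 days of a restart. Understatement of peak severity is the likely direction.

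A reader might go further and conclude that the plan makes imiquimod look better tolerated than it is. The documents do not support that as a result: a severe reaction may persist to the next rating, investigators may grade it anyway, and the number of such visits is unknown. The 10 and 12.5 points are the effect of one missed severe reaction, not an estimate of the bias.

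The timing counts assume that the algorithm is followed and that rest weeks do not lengthen treatment. This is a low-cost improvement that should be made.

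**What to change.** - In Sections 2, 3.4 and 6.4 and the schedule, require the same four-level rating at every unscheduled toxicity visit, before the dose algorithm is applied. In Section 4.4.2, require it at the post-withdrawal visit.
- Reconcile the Visit 2 mark in the schedule with Sections 2, 3.4 and 6.2.
- Define the safety endpoint in Section 3.4 as each patient's worst grade at any scheduled or unscheduled visit from first application.
- In Sections 7.2 and 7.3, summarise safety in all treated patients rather than only protocol completers. Without this, the added ratings could be left out of the analysis.
- Report beside it the number of patients with a rest period, a frequency reduction, or a permanent stop for intolerability. Show the week-8 rating separately as off-drug.

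The cost is wording in these sections and minor extra recording at visits the plan already foresees. Sample size, alpha and power do not change, and no treatment rule is altered. The downside is that reported tolerability may look less favourable.
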